3.2. Subject Restrictions

Lifestyle, Medications and Treatments
 
During the entire study (screening – Last Subject Last Visit (LSLV)):
 
 1. Subjects must not apply any leave-on cosmetics (e.g. creams, lotions, oily
--

 GlaxoSmithKline	Document Name	207640 Protocol.doc		
	Type	Version	Document Identifier	Effective Date
	eldo_controlled	2.0; Most-Recent; Effective; CURRENT	090032d580d3df08	11-May-2017 13:45:31
	Reason For Issue	Auto Issue		

- cleansing products) to the test area.
2. Subjects must not apply any detergents (e.g. soaps, shampoos, and bath and shower products) to the test area throughout the entire course of the study.
 3. Subjects must avoid any sun exposure, UV-therapy and/or artificial tanning.

3.3. Type and Planned Number of Subjects

Healthy males and females aged between 18-70 years (inclusive) with Fitzpatrick phototype I, II or III, an ITA° value greater than 28° and who are untanned on the test area will be recruited for this study. The study will contain a population of subjects of more than one Fitzpatrick phototype.

The SPF result for the test product and for the reference sunscreen formulation is calculated as the arithmetical mean of all valid SPF_i values. The minimum number of valid SPF_i values shall be 10 and the maximum number of valid SPF_i values 20. A maximum of 5 results may be excluded from the calculation of the mean SPF, but each exclusion shall be justified. A sixth invalid result automatically invalidates the whole test for that test product and no SPF can be calculated for it. In addition, if the mean SPF obtained for the reference sunscreen formulation (P3) does not fall within the acceptance limits of the reference values (i.e. between SPF 13.7-17.7, inclusive) then the entire test shall be rejected.

The statistical criterion for all SPF measurements is that the 95% confidence interval (CI) of the mean SPF measured shall fall within a range of ±17 % of the mean measured SPF. This applies to test and reference sunscreen products.

Consequently, the actual number of subjects tested is defined as the number (minimum 10) required to produce a mean test product SPF with a 95% CI which falls within a range of ±17 % of the measured mean SPF for the test product and a mean reference product SPF between 13.7-17.7, inclusive, and which has a 95 % CI which falls within the range of ±17 % of the measured mean SPF for the reference product.

A minimum of 10 valid results is only sufficient if the statistical criterion is fulfilled for the test product and positive control. If not, the number of subjects is increased from 10, for both the test product and positive control, until the statistical criterion is met, with up to a maximum of 20 valid results.

Subjects will be recruited from the site database and via advertisement in local papers.

 GlaxoSmithKline	Document Name	207640 Protocol.doc		
	Type	Version	Document Identifier	Effective Date
	eldo_controlled	2.0; Most-Recent; Effective; CURRENT	090032d580d3df08	11-May-2017 13:45:31
	Reason For Issue	Auto Issue		

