
 1. Current / Concomitant Medication* 2. Continued Eligibility* 3. Test Product and Reference Sunscreen Application to Randomly Assigned Test Sites on the Back 4. UV Exposure of Test Product Treated, Reference Sunscreen Formulation Treated and Unprotected Test Sites. 5. Adverse Events 
*Not required if Visit 4 is combined with Visit 3

Visit 5 – MEDp and MEDu determination and SPF calculation for test and reference sunscreen

The following assessments will be conducted:
 
 1. Current / Concomitant Medication 2. Continued Eligibility 3. Visual Grading of Exposure Sub-Sites to Determine MEDp and MEDu and calculate SPF* 4. Adverse Events 5. Subject Discharge from Study 
* Visual grading of skin must occur 16-24 hours after completion of the test irradiation procedure

Type and Planned Number of Subjects

Healthy volunteers aged between 18-70 years (inclusive) with Fitzpatrick phototype I, II or III, an ITA° value greater than 28° and who are untanned on the test area will be recruited for this study. The study will contain a population of subjects of more than one Fitzpatrick phototype.

To complete the study successfully, the minimum number of valid individual sun protection factor (SPFi) results will be 10 and the maximum number of valid SPFi results will be 20 for both the test product and positive control. In order to achieve between 10 and 20 valid SPFi results, a maximum of 5 individual invalid results may be excluded from the calculation of the mean SPF. Consequently, the actual number of subjects used for the study will fall between a minimum of 10 and a maximum of 25 (i.e. a maximum of 20 valid SPFi results plus 5 rejected invalid results).

In order to determine the number of test subjects, the 95% confidence interval (95% CI) of the mean SPF shall be taken into account. A minimum of 10 subjects shall be tested. The test shall be considered valid for the first 10 subjects if the resulting range of the 95% CI of the mean SPF is within ±17% of the mean SPF. If it is not within ±17% of the mean SPF, the number of subjects shall be increased stepwise from the minimum number of 10 until the 95% CI statistical criterion is met (up to a maximum

 GlaxoSmithKline	Document Name	207640 Protocol.doc		
	Type	Version	Document Identifier	Effective Date
	eldo_controlled	2.0; Most-Recent; Effective; CURRENT	090032d580d3df08	11-May-2017 13:45:31
	Reason For Issue	Auto Issue		

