9.3.2. Primary Analysis

The SPF_i of each product on each subject is calculated from the individual MED on unprotected skin (MED_u) and the individual MED on product protected skin (MED_p) according to Equation 2:

$$SPF_i = \frac{MED(\text{protected skin})}{MED(\text{unprotected skin})} = \frac{MED_p}{MED_u} \quad (\text{Equation 2})$$

SPF_i values are expressed to 1 decimal place.

The SPF of the product is the arithmetical mean of the valid individual SPF_i values obtained from the total number, *n*, of subjects used, expressed to one decimal place as per Equation 3.

$$SPF = \frac{(\sum SPF_i)}{n} \quad (\text{Equation 3})$$

Its standard deviation, *s*, is given by Equation 4.

$$s = \sqrt{\frac{\left[\sum (SPF_i^2) \right] - \left[\frac{(\sum SPF_i)^2}{n} \right]}{(n-1)}} \quad (\text{Equation 4})$$

The 95 % confidence interval (95 %CI) of the mean SPF is expressed by Equation 5.

$$95 \%CI = SPF - c \text{ to } SPF + c \quad (\text{Equation 5})$$

Where *c* is calculated as:

$$c = (t \text{ value}) \times SEM = \frac{(t \text{ value}) \times s}{\sqrt{n}} \quad (\text{Equation 6})$$

$$c = \frac{t \times s}{\sqrt{n}} \quad (\text{Equation 7})$$

$$CI[\%] = \frac{100 \times c}{SPF} \quad (\text{Equation 8})$$

And where

	Document Name	207640 Protocol.doc		
	Type	Version	Document Identifier	Effective Date
	eldo_controlled	2.0; Most-Recent; Effective; CURRENT	090032d580d3df08	11-May-2017 13:45:31
	Reason For Issue	Auto Issue		

SEM is the standard error of the mean;

n is the total number of subjects used;

t is the t value from the “two-sided” Student- t distribution (Table 1) at a probability level $p = 0.05$ and with degrees of freedom $\nu = (n - 1)$.

Table 1 – Student- t Distribution

N	10	11	12	13	14	15	16	17	18	19	20
t value	2.262	2.228	2.201	2.179	2.160	2.145	2.131	2.120	2.110	2.101	2.093

The mean SPF of the reference sunscreen formulation (P3) used in the test shall fall within the defined acceptance limits (lower limit, SPF 13.7; upper limit, 17.7) and shall comply with the $\pm 17\%$ statistical criterion. If the acceptance SPF limits are not met, the entire test shall be rejected.

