2.4 Analysis of Sun Protection Factor (SPF)

2.4.1 Primary efficacy endpoint

2.4.1.1 Primary endpoint definition

The primary analysis will be based on sun protection factor (SPF). Individual SPF for each subject (SPFi) is defined as the ratio of his/her minimal erythemal dose of protected skin (MEDp) over unprotected skin (MEDu), i.e., SPFi = MEDp / MEDu (keeping 1 decimal place for individual SPF). As each subject will have both test product and reference product applied on two sites of dorsum together with an unprotected site, each subject will provide two individual SPFs, one for the test product, one for the reference product. The MEDp at two protected sites and MEDu at the unprotected site of each subject determined by a trained grader at Visit 5 will be used in primary analysis.

Summary statistics for SPF, including mean, standard deviation, will be presented by treatment. The 95% CIs for the mean SPFs of the two treatments will be constructed via t-statistic and presented together with summary statistics (Table 14.2.1.1. for Analysis Population). The study will be considered valid if

- the range of the 95% CI of the mean SPF is within ±17% of the mean SPF for each product;
- The mean SPF of the reference sunscreen formulation (P3) used in the test shall fall within the defined acceptance limits (lower limit, SPF 13.7; upper limit, 17.7).

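### Protocol 3.3 and the synopsis put the P3 limits into the definition of the number tested, while every rule for adding subjects uses the ±17% CI alone

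*Protocol*

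**What the plan says.** **Definition of the number tested.** Protocol 3.3 says "the actual number of subjects tested is defined as the number (minimum 10) required to produce" three things: a test-product 95% CI within ±17% of its mean, a P3 mean inside 13.7 to 17.7, and a P3 95% CI within ±17% of its mean. The P3 part reads "and a mean reference product SPF between 13.7-17.7, inclusive, and which has a 95 % CI which falls within the range of" ±17%. The synopsis (Statistical Methods) repeats the sentence.

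**Meaning of the criterion.** One paragraph earlier, 3.3 defines the term: "The statistical criterion for all SPF measurements is that the 95% confidence interval (CI) of the mean SPF measured" lies within ±17% of that mean. The P3 limits are not part of it.

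**Rule for adding subjects.** The paragraph after the definition, in 3.3 and in the synopsis, adds subjects for both products "until the statistical criterion is met, with up to a maximum of 20 valid results". The synopsis section on planned numbers, Protocol 9.1 and SAP 2.9 say the same: "the number of subjects shall be increased stepwise from the minimum number of 10 until the 95% CI statistical criterion is met". SAP 2.8 leaves this procedure to site staff and plans no formal interim analysis.

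**Consequence of a P3 failure.** In 3.3 and the synopsis, if the P3 mean is outside its limits, "then the entire test shall be rejected". Protocol 9.3.2 agrees: "If the acceptance SPF limits are not met, the entire test shall be rejected". SAP 2.4.1.1 lists the limits as a condition for a valid study: "The mean SPF of the reference sunscreen formulation (P3) used in the test shall fall within the defined acceptance limits".

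**The concern.** Suppose both CIs meet ±17% at some n below 20 but the P3 mean is outside 13.7 to 17.7. The definition sentence says the required number has not been reached, so testing continues. The adding rule says testing stops. The rejection rule says the test fails, but not whether it fails at that n or only after up to 20 valid results.

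P3 is included to verify the test procedure. If subjects are added until P3 passes, the check is repeated at each step, and a procedure whose true P3 mean lies outside the limits gets more chances to pass. Site staff apply the stepwise procedure, so the sentence they follow decides the outcome.

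**Working it through.** **Plan's own figures.** The maximum is 20 valid + 5 invalid = 25 subjects. All 11 t values in Table 1 of 9.3.2 reproduce as the two-sided 95% Student t with n−1 degrees of freedom. With CI[%] = 100·t·s/(√n·mean), the criterion is met when the observed CV is at most 17·√10/2.262 = 23.8% at n=10 and 17·√20/2.093 = 36.3% at n=20.

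**Worked example (no CV assumed).** Under Protocol 6.4.4 the unprotected series is set from the provisional MEDu and the P3 series from 16 times it. Both step by 1.25. At nominal doses a P3 SPFi is therefore 16 × 1.25^k: 10.2, 12.8, 16.0, 20.0, 25.0 and so on.

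| n | P3 values | Mean | s | t | c = t·s/√n | CI[%] | P3 in 13.7–17.7? |
|---|---|---|---|---|---|---|---|
| 10 | 5 × 16.0, 5 × 20.0 | 18.0 | 2.108 | 2.262 | 1.508 | 8.4 | No |
| 11 | 6 × 16.0, 5 × 20.0 | 17.8 | 2.089 | 2.228 | 1.403 | 7.9 | No |
| 12 | 7 × 16.0, 5 × 20.0 | 17.67 | 2.060 | 2.201 | 1.309 | 7.4 | Yes |

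If the test-product CI is met throughout, the adding rule stops at n=10 and the test is rejected. The definition sentence continues to n=12 and the test is accepted.

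**How often it matters.** The documents give no CV, test–reference correlation or step size, so these are assumptions. The simulation used 100,000 runs per setting, lognormal SPFi rounded to one decimal, test mean 21, correlation 0.3, and n from 10 to 20 in steps of one.

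- Rule A (CI only): stop at the first n where both CIs are within ±17%, then judge P3 once.
- Rule B (literal definition): stop at the first n where both CIs and the P3 limits are met.

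The disputed state is that both CIs are met and P3 is out. At a true P3 mean of 16:

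| Assumed CV | Runs in disputed state | Accepted, A | Accepted, B |
|---|---|---|---|
| 10% | 0.04% | 99.96% | 100.0% |
| 15% | 1.4% | 98.6% | 99.97% |
| 20% | 4.8% | 95.2% | 99.6% |
| 25% | 8.0% | 90.9% | 97.2% |
| 30% | 8.8% | 76.1% | 81.4% |

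At CV 20%, 91% of the disputed runs are later accepted under B: 95.2% + 0.91 × 4.8% ≈ 99.6%. Those runs use on average 10.6 valid subjects under A and 14.0 under B.

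**Sensitivity at CV 20%, A against B.**

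- True P3 16, correlation 0.5 (20,000 runs): 95.2% against 99.7%.
- True P3 16, steps of 5: 95.8% against 99.4%. Steps of 10: 96.2% against 99.3%.
- True P3 16, SPFi snapped to the 1.25 dose grid: 93.8% against 99.4%.
- True P3 18.0, outside the limits: 42% against 60%. Steps of 5: 42% against 53%. Steps of 10: 42% against 49%.

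**Effect on the reported test SPF (accepted runs, CV 20%).** At true P3 16 the mean is 20.96 under A and 20.98 under B, a shift of 0.02. The largest shift in any setting was 0.07 (21.29 against 21.22, true P3 13.7).

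**The case against.** The best defence is that the working procedure is already identifiable. SAP 2.8 points site staff to the sample size procedure. Protocol 9.1 and SAP 2.9 are that procedure, and both use the CI alone. The paragraph straight after the disputed sentence does the same. The sentence can be read as a summary of what a successful test must show, since it contains no instruction to add subjects. Once n is fixed by the CI rule, Equation 3 takes the mean over all subjects used, so the P3 check falls on that final set. No number or formula is wrong, and the largest acceptance gap quoted assumes a true P3 mean outside the limits.

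Most of this stands. The CI-only reading has the weight of the text behind it, the definition sentence is the outlier, and the practical effect is small. It does not remove the conflict. The sentence is framed as a definition of how many subjects are tested, not as a list of success conditions. The rejection rule is silent on the n at which it applies. SAP section 3 also declares no change from the protocol's planned analysis, although the SAP does not carry the definition sentence.

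**Conclusion.** The concern holds as a minor inconsistency between two stated decision rules. The worked example shows that one data set can be rejected or accepted depending on the sentence followed. It rests only on the protocol's dose steps and equations, and on the test-product CI being met. How often this happens depends on the assumed CV, correlation, distribution and step size. At the expected P3 of 16 the literal definition raises acceptance by at most about 6 percentage points over CVs of 10% to 30% (97.2% − 90.9% = 6.3 points at CV 25%). The gap is wider when the true P3 mean is near or just beyond a limit. The reported test-product SPF is barely affected.

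**What to change.** Reconcile the passages. Unless the ISO standard that Protocol 3.4 commits to says otherwise (it was not available for this review), take the P3 limits out of the definition of the number tested in 3.3 and the synopsis. Then state one rule in 3.3, both synopsis sections, 9.1, 9.3.2, SAP 2.4.1.1 and SAP 2.9, along these lines:

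> Recruitment continues beyond 10 valid results only while either product fails the ±17% CI criterion, to a maximum of 20 valid results. The P3 mean is then compared with its limits once, on that final set of valid results. A P3 mean outside the limits rejects the whole test.

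Confirm this against the standard before finalising. If the standard does require further subjects when P3 is out of limits, write that into 9.1 and SAP 2.9 instead.

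The cost is wording only, with no extra subjects. Compared with 9.1 and SAP 2.9 as written, nothing changes. Compared with the literal reading of 3.3, a sound test (true P3 16, assumed CV 20%) is accepted 95.2% of the time, not 99.6%.

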3.4. Study Design

As UV rays are responsible for most of the Sun's damaging effects on the skin, the erythema protective efficiency of sunscreen products is tested within this range of wavelengths. Therefore, the definition of the spectrum of the UV solar simulator is limited to the terrestrial UV wavelengths, i.e. from 290 nanometers (nm) to 400 nm. Wavelengths below this range (<290 nm) do not occur in terrestrial sunlight and should be excluded, whilst those above this range (>400 nm) may cause undesirable side effects (particularly thermal effects) and should be removed using appropriate devices.

This study is designed to be compliant with international standard ISO 24444:2010 which mandates a controlled product dose of 2.00 ± 0.05 milligrams (mg) per square centimeter (cm²) of test site area.

The dorsum (back) is chosen as the anatomical region for the test. The individual product test sites and the unprotected test site will be delineated within the region between the scapula line and the waist. Skeletal protrusions and extreme areas of curvature will be avoided and test sites will be free from blemishes and have an even colour tone.

The total area of the individual test sites for provisional MEDu determination, product application and the untreated site will be 40 cm² and there will be a minimum distance of 1 centimeter (cm) between the borders of adjacent test sites to ensure no overlap of product and UV exposure. In addition, the minimum distance between borders of each exposure sub-site will be at least 0.8 cm and the distance between any exposure sub-site and any edge of the test site will be at least 1 cm. Test sites will be delineated using a marker and template made from non-absorbent materials in a manner which will not interfere with the test or harm the subject. Prior to product application, test sites may be cleaned by using a dry cotton pad or equivalent.

The positions of the test product and reference sunscreen test sites will be distributed randomly on the backs of subjects over the whole test group in order to reduce error arising from anatomical differences in the skin. The test site used to determine the unprotected minimal erythema dose (MEDu) will be randomised as one of the test sites across the back and across subjects. Test site demarcation, product application and irradiation procedures will be conducted with the subject lying horizontally on their front.

 GlaxoSmithKline	Document Name	207640 Protocol.doc		
	Type	Version	Document Identifier	Effective Date
	eldo_controlled	2.0; Most-Recent; Effective; CURRENT	090032d580d3df08	11-May-2017 13:45:31
	Reason For Issue	Auto Issue		

A reference sunscreen formulation (P3) will be included as a comparator to verify the test procedure.

4. SELECTION OF STUDY POPULATION AND WITHDRAWAL CRITERIA

Specific information regarding warnings, precautions, contraindications, adverse events, and other pertinent information on the GSK investigational product or other study treatment that may impact subject eligibility is provided in the Safety Statement.

Deviations from inclusion and exclusion criteria are not allowed because they can potentially jeopardize the scientific integrity of the study, regulatory acceptability or subject safety. Therefore, adherence to the criteria as specified in the protocol is essential.

4.1. Inclusion Criteria

A subject will be eligible for inclusion in this study only if all of the following criteria apply:

1. CONSENT
Demonstrates understanding of the study procedures, restrictions and willingness to participate as evidenced by voluntary written informed consent and has received a signed and dated copy of the informed consent form
2. AGE
Aged between 18 and 70 years inclusive
3. GENDER
Subject is male or female
4. GENERAL HEALTH
Good general and mental health with, in the opinion of the investigator or medically qualified designee no clinically significant and relevant abnormalities in medical history or upon physical examination
5. SKIN TYPE/CONDITION
A. Subjects with a Fitzpatrick Skin Type of I, II or III
B. Subjects with an ITA° greater than 28°

 GlaxoSmithKline	Document Name	207640 Protocol.doc		
	Type	Version	Document Identifier	Effective Date
	eldo_controlled	2.0; Most-Recent; Effective; CURRENT	090032d580d3df08	11-May-2017 13:45:31
	Reason For Issue	Auto Issue		

4.2. Exclusion Criteria

A subject will not be eligible for inclusion in this study if any of the following criteria apply:

1. PREGNANCY
Women who are known to be pregnant or who are intending to become pregnant over the duration of the study

2. BREAST-FEEDING
Women who are breast-feeding or lactating

3. CONCURRENT MEDICATION/ MEDICAL HISTORY

 A. Subjects having used medication with known photo-toxic and/or photo-sensitizing potential (e.g. hypericum perforatum, antibiotics, blood pressure regulating agents) up to 14 days prior to screening B. Subjects with a history of systemic therapy with anti-inflammatory agents or analgesics (e.g. diclophenac) up to 3 days prior to screening C. Subjects with dermatological conditions D. Subjects with a history of abnormal response to the sun E. Subjects who are tanned or have had sun exposure on the back area in the previous 4 weeks prior to screening F. Subjects having marks, blemishes or nevi or presenting existing sun damage in the test area G. Subjects having excessive hair, moles, tattoos, scars or other imperfections in the test area that could influence the investigation H. Subjects with a history of systemic therapy with immuno-suppressive drugs (e.g. corticosteroids) and/or antihistamines (e.g. anti-allergics) up to 7 days prior to screening I. Subjects with a non-uniform skin colour or hyperpigmentation in the test area J. Subjects with a medical history of dysplastic nevi or melanoma K. Subjects with one of the following illnesses that might require regular systemic medication: Insulin-dependent diabetes, cancer L. Subjects with asthma, unless medicated M. Subjects with an electronic implant (e.g. pace maker, insulin pump, hearing aid) that cannot be removed during irradiation N. AIDS and infectious hepatitis, if known to the subjects

	Document Name	207640 Protocol.doc		
	Type	Version	Document Identifier	Effective Date
	eldo_controlled	2.0; Most-Recent; Effective; CURRENT	090032d580d3df08	11-May-2017 13:45:31
	Reason For Issue	Auto Issue		

4. ALLERGY/ INTOLERANCE

 A. Known or suspected intolerance or hypersensitivity to the study materials (or closely related compounds) or any of their stated ingredients B. Known allergy to latex

5. CLINICAL STUDY/ EXPERIMENTAL PRODUCT

 A. Participation in another clinical study (including cosmetic studies) or receipt of an investigational drug within 30 days prior to screening B. Participation in another clinical study involving UV exposure to the same test site up to 2 months prior to screening C. Previous participation in this study

